8.7.4 CLASSIFICATION OF AN ADVERSE EVENT

8.7.4.1 SEVERITY OF EVENT

For adverse events (AEs) not included in the protocol defined grading system, the Common Terminology Criteria for Adverse Events (CTCAE) Version 5.0 guidelines will be used to describe severity.

- **Grade 1 Mild** – asymptomatic or mild symptoms; clinical or diagnostic observations only; intervention not indicated.
- **Grade 2 Moderate** – minimal, local or noninvasive intervention indicated; limiting age-appropriate instrumental activities of daily living (ADL).
- **Grade 3 Severe** – medically significant but not immediately life-threatening; hospitalization or prolongation of hospitalization indicated; disabling; limiting self-care ADL.
- **Grade 4 Life-threatening** – urgent intervention indicated.
- **Grade 5 Death**

8.7.4.2 RELATIONSHIP TO STUDY INTERVENTION

All adverse events (AEs) will have their relationship to study intervention assessed by a designated blinded study physician at each site. Additional AE adjudication will be provided by one of the Medical Monitors who will review all AEs in an unblinded fashion as is currently recommended by the FDA for SAEs (Guidance for Industry and Investigators Safety: Reporting Requirements for INDs and BA/BE Studies (Section VI.C); December 2012). The Medical Monitors at the CCC will work collaboratively with the reporting investigator to determine if a serious adverse event has a reasonable possibility of having been caused by the study drug or procedure.

The degree of certainty about causality will be graded using the categories below. In a clinical trial, the study product must always be suspect.

- **Definitely Related** – There is clear evidence to suggest a causal relationship, and other possible contributing factors can be ruled out.
- **Probably Related** – There is evidence to suggest a causal relationship, and the influence of other factors is unlikely.
- **Possibly Related** – There is some evidence to suggest a causal relationship (e.g., the event occurred within a reasonable time after administration of the trial medication). However, other factors may have contributed to the event (e.g., the participant's clinical condition, other concomitant events).
- **Probably not related** – A clinical event, including an abnormal laboratory test result, whose temporal relationship to study intervention administration makes a causal relationship

improbable (e.g., the event did not occur within a reasonable time after administration of the study intervention) and in which other drugs or chemicals or underlying disease provides plausible explanations (e.g., the participant's clinical condition, other concomitant treatments).

- **Not Related** – The AE is completely independent of study intervention administration, and/or evidence exists that the event is definitely related to another etiology. There must be an alternative, definitive etiology documented by the clinician.

Administration related adverse events, as outlined in **Section 8.7.3** of the protocol will always be considered suspected adverse reactions if they occur within protocol-defined timeframes (**Section 8.7.3**) of study drug exposure.

8.7.4.3 EXPECTEDNESS

The designated blinded study physician at each site and the Medical Monitor(s) will be responsible for determining whether an AE is expected or unexpected. An AE will be considered unexpected if the nature, severity, or frequency of the event is not consistent with the risk information previously described for the study product as described in the Investigator's Brochure.

8.7.5 TIME PERIOD AND FREQUENCY FOR EVENT ASSESSMENT AND FOLLOW-UP

Blinded study coordinators at each site will collect adverse event information daily during the period from enrollment to study day 7. A blinded study physician who is designated at each site will review AE information collected by the blinded study coordinators and adjudicate any clinical adverse events that occur during the period from enrollment to study day 7. Adverse event collection begins after the patient or surrogate has signed informed consent and has received study drug or undergone study procedures. If a patient experiences an adverse event after consent, but prior to receiving study product, the event will NOT be collected unless the investigator feels the event may have been caused by a protocol procedure. The designated blinded study physician will evaluate any changes in laboratory values and physical signs and will determine if these changes are clinically important. All clinically important adverse events will be recorded in the case report form regardless of attribution to study product. After study day 7, adverse events are not required to be reported unless the investigator feels the events were related to either study product or a protocol procedure.

All AEs including local and systemic reactions not meeting the criteria for SAEs will be captured on the appropriate case report form (CRF). Information to be collected includes event description, time of onset, clinician's assessment of severity, relationship to study product (assessed only by those with the training and authority to make a diagnosis), and time of resolution/stabilization of the event. All AEs occurring while on study must be documented appropriately regardless of relationship. All AEs will be followed to adequate resolution.

Any medical condition that is present at the time that the participant is screened will be considered as baseline and not reported as an AE. However, if the pre-existing medical condition deteriorates at any time between the first study product administration and study day 7, it will be recorded as an AE. Organ failures related to ARDS or the patient's underlying condition that are systematically captured by the protocol should not be reported as adverse events **unless they are considered to be study related**.

Changes in the severity of an AE will be documented to allow an assessment of the duration of the event at each level of severity to be performed. AEs will be followed for outcome information until resolution or stabilization or until 28 days (or hospital discharge whichever occurs first) after enrollment.

For this trial, a subset of adverse events will be considered to be “administration related adverse events”. These “administration related adverse events” will by definition be considered suspected adverse reactions. These events are:

- Acute MI within 48 hours of study drug administration
- Acute stroke within 48 hours of study drug administration
- New onset atrial or ventricular arrhythmia requiring DC cardioversion within 48 hours of study drug administration
- Increased oxygenation requirements defined as: an increase in FiO_2 of ≥ 0.2 **AND** increase in PEEP $\geq 5 \text{ cm H}_2\text{O}$ within 6 hours of study drug administration
- Increase in any protocol-specified measurement of COHb $\geq 10\%$
- Increase in lactate by $\geq 2 \text{ mmol/L}$ within 6 hours of study drug administration

8.7.6 ADVERSE EVENT REPORTING

All clinically important AEs as described in **Section 8.7.5**, will be recorded in the StudyTRAX database. For each AE, an email will be sent to the CCC, site PI, and blinded physician adjudicating AEs at each site. AEs will be summarized using System Organ Class and preferred terms. Tables will show by treatment group the number and percentage of participants experiencing an AE within a System Organ Class or within preferred term category by severity or by relationship to study product. For the calculations in these tables, a participant with multiple AEs within a category will be counted once under the maximum severity or the strongest recorded causal relationship to study product. Formal statistical testing comparing groups is not planned since interpretation of differences must rely heavily upon clinical judgment.

8.7.7 SERIOUS ADVERSE EVENT REPORTING

Site investigators will report all **serious AND unexpected adverse events or reactions**, regardless of relationship to the study intervention, to the CCC by entering the event information into StudyTrax within 24 hours of becoming aware of the event. StudyTrax will automatically send an email alert to the CCC and DCC study leadership. The site investigator should include an assessment of whether there is a reasonable possibility that the study intervention caused the event.

Investigators will also report all **serious AND administration related adverse events** (as described in **Section 8.7.3**) to the CCC by email within 24 hours of becoming aware of the event. An email will also be sent from the StudyTRAX database alerting the CCC to the event. The CCC will review the event and may inform the site to permanently discontinue study drug administration to the subject (**Section 6.1.8**), and may hold enrollment pending Executive Committee (EC) and DSMB review (**Section 10.1.6**). The CCC may also request additional information from the site investigator.

If the event is characterized as **unexpected and related or possibly related to the research** and indicates that there are new or increased risks to subjects, the CCC will notify the MGB IRB within 5 working days/7 calendar days of the date the investigator first becomes aware of the problem according to the MGB IRB requirements.

The CCC will report all **unexpected and study-related deaths** or **life-threatening suspected serious adverse events (SUSAR)** to the FDA within 7 calendar days of receipt. The CCC will report **all deaths occurring during the study hospitalization** and **all serious, unexpected, and study-related adverse events** and **all administration related adverse events** to the DSMB, by email, or telephone, within 7 calendar days of the CCC being notified of the event. A written report will be sent to the DSMB and the FDA within 15 calendar days. Site investigators will also be sent these reports and will follow their local IRB's policy for reporting.

8.8 UNANTICIPATED PROBLEMS

8.8.1 DEFINITION OF UNANTICIPATED PROBLEMS (UP)

An unanticipated problem involving risks to participants or others is defined as any incident, experience, or outcome that meets all of the following criteria:

- Unexpected in terms of nature, severity, or frequency given (a) the research procedures that are described in the protocol-related documents, such as the IRB-approved research protocol and informed consent document; and (b) the characteristics of the participant population being studied;
- Related or possibly related to participation in the research (“possibly related” means there is a reasonable possibility that the incident, experience, or outcome may have been caused by the procedures involved in the research); and
- Suggests that the research places participants or others at a greater risk of harm (including physical, psychological, economic, or social harm) than was previously known or recognized.

8.8.2 UNANTICIPATED PROBLEM REPORTING

Site investigators will report unanticipated problems (UPs) to the PI and CCC within 24 hours. Unanticipated problems will be reported to the SIRB within 5 working days/7 calendar days of the date the investigator first becomes aware of the problem. The UP report will include the following information:

- Protocol identifying information: protocol title and number, PI's name, and the IRB project number;
- A detailed description of the event, incident, experience, or outcome;
- An explanation of the basis for determining that the event, incident, experience, or outcome represents an UP;
- A description of any changes to the protocol or other corrective actions that have been taken or are proposed in response to the UP.

9 STATISTICAL CONSIDERATIONS

9.1 STATISTICAL HYPOTHESES

Hypothesis: We hypothesize that low dose iCO will be safe and well-tolerated and that the CFK equation-based iCO personalized dosing algorithm will be accurate in achieving a target COHb level of 6-8% in patients pneumonia (without ARDS and sepsis or with sepsis without ARDS criteria) and with sepsis-induced ARDS at study entry.

We further hypothesize that precision-based iCO therapy will reduce the severity of pneumonia and ARDS and organ failure by suppressing mitochondrial dysfunction, inhibiting inflammasome activation and necroptosis, and accelerating resolution of inflammation.

Primary Endpoints:

1. The primary endpoint is **safety of iCO**, defined by the incidence of pre-specified administration-related AEs and SAEs.

Administration-related SAEs are: 1) myocardial infarction; 2) stroke; 3) new onset arrhythmia requiring DC cardioversion; 4) worsening hypoxemia^{1,2}; 5) COHb \geq 10%; and 6) increase in lactate by \geq 2 mmol/L.

2. **Accuracy** of the CFK equation-based personalized iCO dosing algorithm to achieve a COHb level of 6-8%.

Secondary Endpoints:

1. Lung Injury Score (LIS) on days 1-5 and day 7
2. PaO₂/FiO₂ ratio on days 1-5 and day 7
3. Oxygenation index (OI) on days 1-5, and 7
4. Dead space fraction (Vd/Vt) on days 1-3 and day 7
5. Sequential Organ Failure Assessment (SOFA) scores on days 1-5, 7, 14, and 28
6. Ventilator-free days at day 28
7. ICU-free days at day 28
8. Hospital-free days to day 60
9. Hospital mortality to days 28 and 60
10. Neurocognitive function at 3 and 6 months

Exploratory Endpoints:

1. Plasma and urine biomarkers of mitochondrial dysfunction (mtDNA)
2. Plasma and urine biomarkers of inflammasome activation (IL-18)
3. Plasma and urine biomarkers of necroptosis (RIPK3)
4. Plasma Lipid mediators (LM) and specialized pro-resolving mediators (SPMs)

9.2 SAMPLE SIZE DETERMINATION

As the primary endpoint of this Phase Ib trial is safety, this sample size of 36 (2:1 CO:placebo) was chosen based on a probability to estimate the mean difference between measured and predicted COHb levels in the CO group within 0.5% with 95% confidence to support the accuracy of the CFK equation.

Our preliminary data from our Phase Ia trial demonstrate that the CFK equation is highly accurate at predicting COHb levels following a 20 minute exposure to 200 ppm iCO ($r=0.916$, $R^2=0.9204$; $p<0.0001$). The mean difference between measured and predicted COHb levels was 0.1467 ± 0.2738 . Using a more conservative estimate of standard deviation (SD)=0.6, we will have >99% probability that 95% confidence intervals around the mean difference between measured and predicted COHb levels will be -0.353% to 0.647%. Our calculation includes an 8% dropout rate.

The goal of the safety evaluation for this study is to identify safety concerns associated with CO administration. The ability of the study to detect administration-related AEs or SAEs can be expressed by the true event rate above which at least one SAE would likely be observed and the true event rate below which no events would likely be observed. Specifically, for the CO arm of the study (n=24), there is a 90% probability of observing at least one AE if the true background rate of that AE is 10% and a 97% probability of observing at least one AE if the true background rate of that AE is 15%. For the placebo arm of the study (n=12), there is an 83% probability of observing at least one AE if the true background rate of that AE is 15% and a 91% probability of observing at least one AE if the true background rate of that AE is 20%. In our Phase Ia trial, there were no administration-related AEs and no SAEs related to study product or procedures.

Probabilities of observing one or more events between the groups are presented in **Table 6** below for a range of possible true AE rates. These calculations provide a more complete picture of the sensitivity of this study design to identify potential safety problems with CO.

Table 6. Probability of observing 1 or more events between the groups for different true AE rates

| CO group | | | Placebo Group | | |
|----------|--------------|-----------------------------|---------------|--------------|-----------------------------|
| n | True AE rate | Power to detect ≥ 1 AE | N | True AE rate | Power to detect ≥ 1 AE |
| 24 | 0.010 | 0.20 | 12 | 0.010 | 0.10 |
| 24 | 0.020 | 0.36 | 12 | 0.020 | 0.20 |
| 24 | 0.035 | 0.54 | 12 | 0.035 | 0.32 |
| 24 | 0.050 | 0.68 | 12 | 0.050 | 0.43 |
| 24 | 0.100 | 0.90 | 12 | 0.100 | 0.69 |
| 24 | 0.150 | 0.97 | 12 | 0.150 | 0.83 |
| 24 | 0.200 | 0.99 | 12 | 0.200 | 0.91 |

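### Section 9.2 prints the 0.5-point tolerance around the Phase Ia mean as if it were the expected 95% CI; the design gives a CI about half that wide, and the criterion alone does not yield 24 CO subjects

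*Combined protocol and SAP*

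**What the plan says.** Section 9.2 names a precision criterion as the basis for the trial's size: "this sample size of 36 (2:1 CO:placebo) was chosen based on a probability to estimate the mean difference" between measured and predicted COHb in the CO group "within 0.5% with 95% confidence to support the accuracy of the CFK equation". Its planning inputs are the Phase Ia result ("The mean difference between measured and predicted COHb levels was 0.1467 ± 0.2738"), an inflated spread ("Using a more conservative estimate of standard deviation (SD)=0.6") and an allowance for loss ("Our calculation includes an 8% dropout rate"). The result is given as "we will have >99% probability that 95% confidence intervals around the mean difference between measured and predicted COHb levels will be -0.353% to 0.647" percentage points.

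The same section then gives the probability of seeing at least one adverse event with 24 CO and 12 placebo subjects, tabulated in Table 6. Section 9.4.2 plans to report the mean predicted-versus-measured difference with its 95% CI for the iCO group. Accuracy of the dosing algorithm is the second primary endpoint in Section 9.1.

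**The concern.** The printed interval has no visible link to SD/√n. It is centred on the Phase Ia mean and extends exactly 0.5 either side, which is the tolerance stated two sentences earlier. A reader will take it as the precision expected for a primary endpoint, and it differs from what SD 0.6 and about 22 to 24 subjects give.

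Two further things are unclear. The sentence promises fixed endpoints for an interval that will be centred on this trial's own mean, so it is not evident what the >99% refers to. And if the size was chosen on this criterion, the criterion should lead to about 24 CO subjects. At stake is whether the stated precision and the stated reason for the sample size can be relied on. The planned analyses are not affected.

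**Working it through.** **Inputs (all Section 9.2).** Phase Ia mean difference 0.1467; planning SD 0.6; tolerance h = 0.5 percentage points; 95% two-sided confidence; CO arm 24; dropout 8%, so 24 × 0.92 = 22.1, taken as 22 evaluable. I assume one independent, roughly normal difference per CO subject.

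**1. The plan's interval.** 0.1467 − 0.5 = −0.353 and 0.1467 + 0.5 = 0.647. This reproduces the printed endpoints exactly, without using the SD or n.

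**2. The plan's >99%.** For a one-sample t interval,

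P(half-width ≤ h) = P(χ² with n−1 df ≤ (n−1) × [h√n / (t(0.975, n−1) × SD)]²).

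At n = 22, t = 2.080 and the bound is 21 × [0.5 × 4.690 / (2.080 × 0.6)]² = 74.2, so the probability is above 0.9999. It is also above 0.9999 at n = 24. Read as a statement about the half-width, >99% reproduces.

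**3. The interval the design gives.** Half-width = t(0.975, n−1) × 0.6/√n, with the sample SD at its planning value.

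| Evaluable CO subjects | Half-width | CI if centred on 0.1467 | 0.5 ÷ half-width | Half-width not exceeded with 99% probability |
|---|---|---|---|---|
| 22 | 2.080 × 0.6/√22 = 0.266 | −0.119 to 0.413 | 1.88 | 0.36 |
| 24 | 2.069 × 0.6/√24 = 0.253 | −0.107 to 0.400 | 1.97 | 0.34 |

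The last column replaces 0.6 by 0.6 × √(χ²(0.99, n−1)/(n−1)). At n = 22 that is 0.6 × √(38.93/21) = 0.817, and 2.080 × 0.817/√22 = 0.362.

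**4. The n that the criterion needs.** By the formula in step 2, P(half-width ≤ 0.5) is 98.8% at n = 14 and 99.6% at n = 15. So 15 evaluable CO subjects suffice. With dropout, 15/0.92 = 16.3, or 17 enrolled, and 17 × 1.5 = 25.5, or about 26 in total at 2:1.

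**5. The printed endpoints read literally.** The probability that the whole 95% CI lies between −0.353 and 0.647, with the true mean set to 0.1467, is by simulation 92% at n = 22 and 95% at n = 24. About 32 evaluable CO subjects would be needed for 99%. A true mean away from 0.1467 lowers these figures.

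**6. 0.5 read as the full width.** With half-width 0.25 and SD treated as known, n = (1.96 × 0.6/0.25)² = 22.1, and 22/0.92 = 23.9, close to the actual arm of 24. But P(half-width ≤ 0.25) is then only 39% at n = 22 and 50% at n = 24, so >99% fails.

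None of these readings gives both 24 CO subjects as the required number and >99%.

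**The case against.** The strongest reply is that the sentence states an assurance, not an expected interval. The section first sets a target of "within 0.5% with 95% confidence", then gives a >99% probability of meeting it, and an assurance bound should be wider than the expected CI. On that reading the probability is correct and the target is exceeded. This stands for the half-width. It does not rescue the endpoints: the text says the intervals will be −0.353 to 0.647, and step 5 shows that containment within those limits falls short of 99%.

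A reader might infer more than the documents support, in three ways.

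- **That 36 is too few.** The discrepancy runs the other way: the expected precision is better than printed, and 36 comfortably meets the 0.5-point target. The >99% is a lower bound, and the text does not call 36 the minimum.
- **That this sentence is the only quantitative support for the size.** Section 9.2 also gives adverse-event detection probabilities for 24 and 12 subjects, and Section 9.4.3 gives detectable differences for the same arms. The precision criterion is, however, the one named as the basis for choosing 36.
- **That the safety table, feasibility or a full-width target really set 36.** The documents say none of these. The full-width arithmetic in step 6 comes close to 24, but it is inference.

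It is also fair that the consequences are limited. The reported CI will be calculated from the trial's own data, and no decision rule uses the printed interval.

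**Conclusion.** The point holds as an error in a stated precision figure for a primary endpoint. The printed interval is 1.9 to 2.0 times as wide as the 95% CI expected from 22 to 24 CO subjects at SD 0.6: half-width 0.5 against 0.27 and 0.25. The >99% is true for the half-width being 0.5 or less and untrue for the printed endpoints (about 92% and 95%). The criterion named as the basis for 36 is met by about 17 enrolled CO subjects, so on its own it does not yield 24.

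The error is conservative and does not show a shortfall in sample size. The figures rest on the plan's SD of 0.6, on 8% dropout applied to the CO arm, and on one independent difference per subject. If the Phase Ia SD of 0.2738 held, the half-width at n = 22 would be 0.12 and the printed interval would be further still from the expected one.

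**What to change.** In Section 9.2, delete the fixed endpoints and write: *With 22 evaluable CO subjects and SD 0.6, the expected 95% CI half-width is 0.27 points (0.36 or less with 99% probability; 0.5 or less with >99% probability).*

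Say explicitly that the 0.5-point target is a half-width, or, if a full width was meant, restate the assurance to match. Because the 0.5-point criterion alone does not lead to 24 CO subjects, the sponsor should also state the actual basis on which 36 was chosen; that basis should come from the sponsor's records and not be inferred from the arithmetic.

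The cost is one paragraph. The stated precision improves, and the sample size, conduct and planned analyses stay as they are.

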1.4 DEFINITIONS

Acute Kidney Injury: Acute kidney injury network Stage 3 disease, defined as a threefold increase in creatinine from baseline or the need for dialysis

Completing 48 hours of UAB (from weaning form): Defined as the date (calendar day) that the subject reaches exactly 48 hours of UAB. Example: if subject meets UAB at 1900 on 6/1/06 and does not return to AB, then the date of completing 48 hours of UAB would be 6/3/06.

Date of first UAB (from Study Termination form): Defined as the first day that the subject is on UAB from midnight to midnight. Example: if subject meets UAB at 1900 on 6/1/06, then the date of first UAB would be 6/2/06, as long as subject does not return to AB on 6/2/06.

Day zero: Defined as day of randomization. Study days are calendar days.

Drug held/hold drug: Study medication withheld for 24 hours.

Drug permanently discontinued: Study medication stopped for remainder of the trial.

Enrollment: All randomized participants will be included in the intent-to-treat (ITT) population. All randomized subjects who receive at least one dose of study product (CO vs. placebo) will be included in the safety analyses (*ie.* modified ITT). For secondary and exploratory endpoints, subjects may also be analyzed according to the number of study drug doses completed. Because some patients may withdraw or have a change in clinical status precluding dosing of study drug (eg. post-randomization lactic acidosis), we may randomize additional patients to achieve the enrollment goal of 36 patients who are randomized and treated with at least one dose of the study drug. We expect this to be an uncommon occurrence. Patients who are randomized but do not undergo any study procedures or study treatment will not be included in the study analysis.

Extubation: Removal of an orotracheal, nasotracheal tube, or unassisted breathing with a tracheostomy.

Home: level of residence or health care facility where the patient was residing prior to hospital admission

Hospital Mortality to Day 60: This primary endpoint includes all deaths following randomization in any health care facility prior to discharge “home” until study day 60. Study subjects still in a health care facility at study day 61 are considered alive for this endpoint.

Interruption of Dosing During Drug Administration: Study medication prematurely stopped prior to 90 minutes.

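### Section 9.2 and Table 6 label the safety-detection probabilities n=24 and n=12, but every printed figure is the value for n=22 and n=11

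*Combined protocol and SAP*

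**What the plan says.** Section 9.2 makes two separate calculations. The first concerns the precision of the measured-minus-predicted COHb difference. It is the stated basis for the trial's size ("this sample size of 36 (2:1 CO:placebo) was chosen" on that ground), and its paragraph ends with "Our calculation includes an 8% dropout rate".

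The second concerns safety and begins in the next paragraph. It reports, by arm, the probability of observing at least one event for a given true rate. It states that "for the CO arm of the study (n=24), there is a 90% probability of observing at least one AE if the true background rate" is 10%, and gives 97% at 15%. "For the placebo arm of the study (n=12), there is an 83% probability of observing at least one AE" at a true rate of 15%, and 91% at 20%. Table 6 extends this to seven rates per arm, with the arm size printed in every row. Two rows read "24 | 0.010 | 0.20 | 12 | 0.010 | 0.10" and "24 | 0.100 | 0.90 | 12 | 0.100 | 0.69". The safety paragraph does not mention dropout.

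Three other sections bear on the denominator. Section 9.3 puts every randomized subject who receives at least one dose into the safety analyses. Section 1.4 (Enrollment) allows extra randomization to "achieve the enrollment goal of 36 patients who are randomized and treated with at least one dose of the study drug". Section 7.2 says that undosed subjects may be replaced, and that dosed subjects who later withdraw are not.

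**The concern.** Safety is the first primary endpoint, and the 9.2 text with Table 6 is where the plan quantifies what that endpoint can detect in 24 and 12 subjects. A reader who puts the printed n into the standard formula cannot recover any printed figure. Either the n or the probabilities must change, and nothing in the safety paragraph says which was meant. The amendment history (10.3) records that this text and table were revised in version 2.0 to correct the probability calculations, so the present figures are the revised ones.

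**Working it through.** **Inputs.** Arm sizes 24 and 12, true rates and printed probabilities: 9.2 text and Table 6. Dropout of 8%: 9.2, COHb paragraph.

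**Formula.** For independent subjects with true event rate p, P(at least one event among n) = 1 - (1-p)^n.

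**Step 1: which n reproduces the printed figures?** Removing 8% gives 24 × 0.92 = 22.08 and 12 × 0.92 = 11.04, that is, 22 and 11 as whole numbers. For example, for CO at 10%, 1 - 0.90^22 = 0.9015, printed 0.90. For placebo at 15%, 1 - 0.85^11 = 0.8327, printed 0.83.

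**Step 2: the labelled n.** For CO at 10%, 1 - 0.90^24 = 0.9202. For placebo at 15%, 1 - 0.85^12 = 0.8578.

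CO arm:

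| True rate | Printed | n=22 | n=24 | Shortfall against n=24 (points) |
|---|---|---|---|---|
| 0.010 | 0.20 | 0.1984 | 0.2143 | 1.4 |
| 0.020 | 0.36 | 0.3588 | 0.3842 | 2.4 |
| 0.035 | 0.54 | 0.5433 | 0.5747 | 3.5 |
| 0.050 | 0.68 | 0.6765 | 0.7080 | 2.8 |
| 0.100 | 0.90 | 0.9015 | 0.9202 | 2.0 |
| 0.150 | 0.97 | 0.9720 | 0.9798 | 1.0 |
| 0.200 | 0.99 | 0.9926 | 0.9953 | 0.5 |

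Placebo arm:

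| True rate | Printed | n=11 | n=12 | Shortfall against n=12 (points) |
|---|---|---|---|---|
| 0.010 | 0.10 | 0.1047 | 0.1136 | 1.4 |
| 0.020 | 0.20 | 0.1993 | 0.2153 | 1.5 |
| 0.035 | 0.32 | 0.3242 | 0.3479 | 2.8 |
| 0.050 | 0.43 | 0.4312 | 0.4596 | 3.0 |
| 0.100 | 0.69 | 0.6862 | 0.7176 | 2.8 |
| 0.150 | 0.83 | 0.8327 | 0.8578 | 2.8 |
| 0.200 | 0.91 | 0.9141 | 0.9313 | 2.1 |

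**Step 3: count the matches.** At two decimals, 22 and 11 reproduce 14 of 14 cells, and 24 and 12 reproduce none. The CO cell at 0.20 is included in that count, because 0.9953 rounds to 1.00, not 0.99. For CO, n=23 matches only 1 of 7. Truncation does not explain the gap either: with n=24 the first CO cell would truncate to 0.21, not 0.20. The four percentages in the text (90, 97, 83, 91) are the corresponding table cells, so they carry the same mismatch.

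**Step 4: express it as a detectable rate.** The true rate that gives a 90% chance of at least one event is 1 - 0.1^(1/n). This is 9.1% for n=24 and 9.9% for n=22. The text's 10% fits the smaller number.

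**The case against.** The strongest reply is that the allowance is disclosed. The 8% dropout stands in the same section, one paragraph earlier, and a reader who applies it to both arms recovers 22 and 11. Some loss is also conceivable. Replacement of undosed subjects is permitted, not required. A dosed subject who withdraws is not replaced, and data collection after withdrawal needs explicit permission (7.2), so event capture to day 7 (8.7.5) could be incomplete for that subject.

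Part of this stands. A conservative allowance is defensible, the figures are correct for 22 and 11, and it would be unfair to say that the dropout was hidden. What does not stand is the labelling. The dropout sentence closes the COHb calculation and is not tied to the event probabilities. The safety paragraph then restates 24 and 12, as does every row of the table. A dosed subject who withdraws also stays in the safety set under 9.3.

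A reader might go further and infer that the safety evaluation is weaker than claimed, or that 36 subjects is the wrong number. The documents support neither. Each printed value is lower than the value for its stated n, and 9.2 bases the size of 36 on COHb precision. The DSMB provisions (9.4.6, 10.1.6) refer to none of these probabilities.

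**Conclusion.** The mismatch is certain: all 14 cells and all four text percentages are wrong for the n printed beside them. That they were computed with 22 and 11 is an inference from the exact match and the 8% dropout; the protocol does not say so. The planned denominators are 24 and 12, provided that undosed subjects are in fact replaced and the 2:1 split holds among those dosed.

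The size is modest. The printed figures understate detection by 0.5 to 3.5 percentage points, and by more than 2 points in 9 of the 14 cells. The error is conservative and changes neither the sample size nor any analysis. It should still be corrected, because it sits in the justification for the primary safety endpoint.

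**What to change.** Make label and calculation agree, in the text and in Table 6 together.

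- **Preferred:** keep n=24 and n=12 and print their values. CO: 0.21, 0.38, 0.57, 0.71, 0.92, 0.98, >0.99 (0.995). Placebo: 0.11, 0.22, 0.35, 0.46, 0.72, 0.86, 0.93. The text then becomes 92% and 98% for CO at true rates of 10% and 15%, and 86% and 93% for placebo at 15% and 20%.
- **Otherwise:** relabel the columns and the text as n=22 and n=11, state that an 8% allowance was applied to the safety calculation, and explain why it is needed when the safety set is all dosed subjects and the enrollment goal is counted in dosed subjects.

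The cost is one table and one paragraph. Design, conduct and analysis do not change.
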